3.2 Primary Study Endpoints

For Phase Ib, the primary endpoint is identification of toxicities, tolerability and definition of a recommended phase II dose (RP2D) of Q3WK infusions of CDX-3379 in combination with once daily oral administration of trametinib.

For Phase II, the primary endpoint is an estimation of the overall response rate and duration of response in patients treated with CDX-3379 in combination with trametinib in *NRAS* mutant and WT melanoma.

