4.1 Inclusion Criteria

1. Read, understood, and provided written informed consent and, if applicable, Health Insurance Portability and Accountability Act (HIPAA) authorization after the nature of the study has been fully explained and must be willing to comply with all study requirements and procedures.
2. Male or female patients who are 18 years of age or older.
3. Patients with a diagnosis of histologically confirmed advanced (defined as unresectable stage III or IV) melanoma with the *NRAS* Q61 mutation or *BRAF/NRAS* WT who are refractory to or intolerant of existing therap(ies) known to provide clinical benefit for their condition, including anti PD-1 and/or CTLA-4 agent.
 - Any CLIA certified mutation testing is acceptable to document mutation status.
4. Patients must have adequate cardiac function as demonstrated by a left ventricular ejection fraction (LVEF) $\geq 50\%$ as determined by a multigated acquisition (MUGA) scan or echocardiogram.
5. Patients must have archival tissue and at least one disease site amenable to biopsy:
 - For phase Ib, all patients will undergo fresh tumor biopsy
 - For phase II, five patients with *NRAS* mutation and five patients with *BRAF/NRAS* WT melanoma will undergo fresh tumor biopsy
6. Measurable (target) disease by Response Evaluation Criteria In Solid Tumors (RECIST 1.1) criteria. Target lesions selected for tumor measurements should be those where additional (eg palliative) treatments are not indicated or anticipated.
 - Measurable disease per RECIST 1.1 requirements: defined as longest diameter to be recorded for non-nodal lesions $> 10\text{mm}$ and short axis for nodal lesions $> 15\text{ mm}$ using conventional techniques
7. All residual toxicity related to prior radiotherapy or anticancer therapies (excluding alopecia, grade 2 fatigue, vitiligo or endocrinopathies on stable replacement therapy) must resolve to grade 1 severity or less (or returned to baseline) prior to receipt of study treatment.
8. Adequate electrolytes, liver, renal, and hematology function as defined below:
 - a. Hemoglobin $\geq 9\text{ g/dL}$
 - b. Absolute neutrophil count $\geq 1500/\text{mm}^3$
 - c. Platelet count $\geq 100,000/\text{mm}^3$
 - d. Aspartate aminotransferase (AST) and alanine aminotransferase (ALT) $\leq 2.5 \times$ upper limit of normal (ULN) ($\leq 5 \times$ ULN for cases involving liver metastasis)
 - e. Bilirubin $\leq 1.5 \times$ ULN ($\leq 5 \times$ ULN for cases of documented or suspected Gilbert's disease)

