4.2 Exclusion Criteria

Patients will be excluded from the study for any of the following reasons:

1. Received CDX-3379 or other anti-ErbB3 targeted agents previously.
2. Received trametinib or other MEK inhibitor agents previously.
3. Any concurrent chemotherapy, radiotherapy, immunotherapy, biologic or hormonal therapy for cancer treatment. Concurrent use of hormones for non-cancer related conditions (e.g., insulin for diabetes and hormone replacement therapy) is acceptable.
4. Other prior malignancy active within 2 years, except for localized prostate cancer, cervical carcinoma in situ, non-melanomatous carcinoma of the skin, stage 1 differentiated thyroid cancer or ductal carcinoma in situ of the breast that has/have undergone curative surgery or radiation.

CONFIDENTIAL

5. Active central nervous system (CNS) metastases are excluded. Known brain metastases must have been previously treated and asymptomatic for 2 weeks and not progressive in size or number for 4 weeks prior to enrollment, documented via scans. Continued use of anticonvulsants (in the absence of any suspicion of progressive brain metastases) is acceptable. Patients must currently be on a stable, lowest possible dose of steroids.
6. Radiation therapy within 14 days prior to the first scheduled dose in this study, including, in addition (if necessary), the timeframe for resolution of any actual or anticipated toxicities from such radiation.
7. Known HIV, hepatitis B or hepatitis C infection, or active infection requiring systemic intravenous therapy.
8. History or current evidence of retinal vein occlusion (RVO) or current risk factors for RVO (e.g. uncontrolled glaucoma or ocular hypertension, history of hyper viscosity or hypercoagulability syndromes).
9. Use of any monoclonal based therapies within 4 weeks (excluding cetuximab which does not require a wash-out), and all other immunotherapy (tumor vaccine, cytokine, or growth factor given to control the cancer) within 2 weeks, prior to the first dose of study treatment.
10. Chemotherapy within 4 weeks (except for bis-chlorethynitrosurea (BCNU), which must have been completed a minimum of 6 weeks) prior to starting therapy.
11. Major surgery within 4 weeks prior to the first dose of study treatment. Surgery requiring local/epidural anesthesia must be completed at least 72 hours before study drug administration and patients should be recovered.

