5.5 Subject Compliance Monitoring

CDX-3379 will be administered by study staff, and details regarding each administration will be recorded in the subject's medical record and the CRFs. Trametinib will be self-administered, and a medication diary will be provided to subjects.

CONFIDENTIAL

This material is the property of the NYU School of Medicine and Langone Medical Center. Do not disclose or use except as authorized in writing by the study sponsor

5.6 **Prior and Concomitant Therapy**

No other investigational agents or concurrent therapy for melanoma will be allowed during treatment on this clinical trial.

There are no restrictions on the number of prior therapies, however, subjects may not have been treated previously with an ERBB3 or MEK inhibitor.

Drug Interactions: No formal drug interaction studies have been conducted with trametinib. Trametinib is not a substrate of CYP enzymes or efflux transporters P-gp or BCRP *in vitro*. Based on *in vitro* studies, trametinib is not an inhibitor of CYP450 including CYP1A2, CYP2A6, CYP2B6, CYP2C9, CYP2C19, CYP2D6, and CYP3A4 or of transporters including OATP1B1, OATP1B3, P-gp, and BCRP at a clinically relevant systemic concentration of 0.04 µM. Trametinib is an inhibitor of CYP2C8 *in vitro* (trametinib package insert).

Trametinib is an inducer of CYP3A4 *in vitro*. Based on cross-study comparisons, oral administration of trametinib 2mg once daily with everolimus (sensitive CYP3A4 substrate) 5 mg once daily, had no clinically important effect on the AUC and C_{max} of everolimus (trametinib package insert).

In general, concomitant medications and therapies deemed necessary for the supportive care (e.g., such as anti-emetics, anti-diarrhea) and safety of the subject are allowed.

Subjects are permitted to use the following medications during study treatment:

- Medications to prevent or treat nausea or vomiting.
- Anti-diarrheal medications (e.g., loperamide) for subjects who develop diarrhea.
- Pain medication to allow the subject to be as comfortable as possible.
- Bone targeted therapies (e.g., bisphosphonates, denosumab) to treat bone metastases or to prevent skeletal related events.
- Palliative radiotherapy: any radiotherapy must be listed on the 'Surgical and Medical Procedures' eCRF.
- Immunosuppressive agents to treat suspected AEs.
- Nutritional support or appetite stimulants (e.g., megestrol).
- Oxygen therapy and blood products or transfusions.

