- Limited-field palliative radiotherapy to non-target lesion(s) may be allowed as concomitant therapy. Such local therapies administered during the study treatment
- Inactivated vaccines.
- The subject must be told to notify the investigational site about any new medications he/she takes after the start of the study drug. All medications (other than study drug) and significant non-drug therapies (including physical therapy, herbal/natural medications and blood transfusions) administered during the study must be listed on the Concomitant Medications or the Procedures and Surgical and Medical Procedures eCRF.

5.7 **Blinding of Study Drug**

This is an open label, non-randomized study. There is no blinding of treatments.

5.8 **Receiving, Storage, Dispensing and Return**

5.8.1 **Receipt of Drug Supplies**

Upon receipt of the of the study treatment supplies, an inventory must be performed and a drug receipt log filled out and signed by the person accepting the shipment. It is important that the designated study staff counts and verifies that the shipment contains all the items noted in the shipment inventory. Any damaged or unusable study drug in a given shipment (active drug or comparator) will be documented in the study files. The investigator must notify study sponsor of any damaged or unusable study treatments that were supplied to the investigator's site.

CONFIDENTIAL

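### Section 5.6 does not say which of its radiotherapy statements governs, and no passage says how a target lesion irradiated on study is scored for the phase II response endpoint

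*Combined protocol and SAP*

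**What the plan says.** Section 5.6 (Prior and Concomitant Therapy) has three operative statements that bear on radiotherapy during treatment.

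- The opening sentence: "No other investigational agents or concurrent therapy for melanoma will be allowed during treatment on this clinical trial".
- An entry in the list of permitted treatments: "Palliative radiotherapy: any radiotherapy must be listed on the" procedures eCRF. Recording is the only condition.
- A later entry in the same list: "Limited-field palliative radiotherapy to non-target lesion(s) may be allowed as concomitant therapy". The sentence after it, "Such local therapies administered during the study treatment", has no predicate in the supplied text and so states no rule.

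Two eligibility criteria are also relevant. Exclusion 3 in section 4.2 lists "Any concurrent chemotherapy, radiotherapy, immunotherapy, biologic or hormonal therapy for cancer treatment". Inclusion 6 in section 4.1 says "Target lesions selected for tumor measurements should be those where additional (eg palliative) treatments are not indicated or anticipated".

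For phase II, section 3.2 says "the primary endpoint is an estimation of the overall response rate and duration of response". Section 6.7 (footnote 5) has disease evaluated by RECIST 1.1. Section 7.2 counts patients with a partial response or better: at least 3 of 19 to continue an arm, and at least 10 of 36 to reject the null hypothesis.

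**The concern.** A site with a painful target lesion can read the unrestricted entry in good faith, irradiate the lesion, record it and stay on protocol. At the next scan the lesion may be smaller because of the radiation, and that measurement enters the target sum. Neither section 7.2 nor the RECIST reference in 6.7 is accompanied by an instruction for this case. The patient can therefore be counted as a responder to the drugs. Radiation to a growing lesion could also delay recorded progression and lengthen duration of response and PFS.

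Both errors favour the combination. The trial is open-label and non-randomised, progression is assessed locally by the investigator (sections 2, 4.5.1 and 5.4.4), no central reading is described, and there is no concurrent control to absorb the bias. Disease is evaluated every 12 weeks (section 6.4), or sooner at the physician's discretion (section 6.7), so a lesion could be irradiated before the first post-baseline scan.

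**Working it through.** **Reading the passages together**

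| Place | What it does | Limit on the lesion |
|---|---|---|
| 5.6, opening | Bans concurrent melanoma therapy; radiotherapy not named | Not stated |
| 5.6, first radiotherapy entry | Permits palliative radiotherapy, with a recording duty | None |
| 5.6, second radiotherapy entry | May permit limited-field palliative radiotherapy | Non-target only |
| 4.2, exclusion 3 | Bars concurrent radiotherapy for cancer, at entry | Not stated |
| 4.1, inclusion 6 | Guides the choice of target lesions at baseline | Target lesions |

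If the second radiotherapy entry governs, the first should carry its limit. If the first governs, that limit has no force. Sections 5.6, 6 and 7 contain no rule for an irradiated target lesion in response, duration of response or PFS. On-study radiotherapy is not among the reasons for withdrawal in 4.5.1, although that list is not exhaustive.

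**How sensitive the decision rule is**

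The plan gives no figure on this point, so there is none to reproduce. Inputs:

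- True response rate p: 0.15 for *NRAS* mutant and 0.10 for WT, the single-agent rates in section 7.2.
- Stage 1: continue with at least 3/19. Final: at least 10/36 (section 7.2).
- f: the share of true non-responders counted as responders because of radiotherapy. **This is an assumption.** The documents give no value; 1%, 2%, 5% and 10% are shown.

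Apparent response rate: q = p + f(1 − p). For p = 0.15 and f = 0.05, q = 0.15 + 0.05 × 0.85 = 0.1925.

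Chance of continuing: 1 − Σ C(19,x) q^x (1 − q)^(19−x), x = 0 to 2. For q = 0.15 this is 1 − (0.0456 + 0.1529 + 0.2428) = 0.559.

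Chance of passing the full rule: Σ P(X = x) × P(Y ≥ 10 − x), x = 3 to 19, with X binomial (19, q) and Y binomial (17, q).

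| p | f | q | At least 3/19 | Full rule |
|---|---|---|---|---|
| 0.15 | 0 | 0.150 | 0.559 | 0.035 |
| 0.15 | 1% | 0.1585 | 0.599 | 0.048 |
| 0.15 | 2% | 0.167 | 0.637 | 0.065 |
| 0.15 | 5% | 0.1925 | 0.738 | 0.138 |
| 0.15 | 10% | 0.235 | 0.858 | 0.328 |
| 0.10 | 0 | 0.100 | 0.295 | 0.002 |
| 0.10 | 5% | 0.145 | 0.534 | 0.028 |

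For scale, f = 5% at p = 0.15 means 19 × 0.85 × 0.05 = 0.81 false responders expected per arm in stage 1; f = 1% means 0.16.

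Section 3.1 stops an arm at three or fewer responses, which conflicts with 7.2. That is a separate matter. Under that boundary (at least 4/19 to continue), f = 5% at p = 0.15 moves the chance of continuing from 0.316 to 0.512, so the sensitivity does not depend on which boundary is meant.

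**The case against.** The strongest reply is that the two radiotherapy entries fit together: the first sets a recording duty and the second sets the scope. A site that used the first alone would have to ignore another entry in the same list. This reading is reasonable, but the text does not state it, and the first entry stands as a permission in its own right.

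Second, there are safeguards. Inclusion 6 steers target-lesion selection away from lesions where palliative treatment is indicated or anticipated. Section 4.5.1 allows treatment to end for clinical deterioration, so a growing, painful lesion may already take the patient off treatment. Both points stand and lower the risk. However, inclusion 6 applies at selection and is silent on a lesion that becomes symptomatic later, and 4.5.1 leaves the decision to the investigator.

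Third, section 7.2 leaves detailed methods to a SAP due before database lock, which could hold such a rule. But nothing requires that SAP before the 19-patient decision, and the lesion treated has to be recorded while the data are being collected.

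Fourth, f is not a radiotherapy rate. A false responder needs a target lesion irradiated before any response, enough shrinkage in the whole target sum, and no progression elsewhere. The true value could be very small. This stands, and is why the lower values are shown.

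A reader might go further and infer that 5.6 holds four mutually incompatible rules. It does not: it has three statements and an incomplete sentence, which may be a loss in text extraction. Exclusion 3 sits in 4.2 and governs entry. A reader might also infer that the plan directs radiation shrinkage to be counted as response. It does not direct it; it fails to prevent it.

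**Conclusion.** The point holds as an unreconciled set of statements combined with a missing scoring rule. Following the plan as written can bias the phase II primary endpoint in favour of the combination.

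The size cannot be fixed from the documents. At a true rate of 0.15, the probability of passing the full rule is about 1.4 times its nominal value with 1% misclassified (0.048/0.035) and about 4 times with 5% (0.138/0.035). At 0.10, the stage 1 effect of 5% is large (0.29 to 0.53), but the chance of passing the full rule stays small (0.002 to 0.028). These figures assume independent patients, a constant f and the boundaries in 7.2. They show that a few misattributed responses matter; they do not predict that such responses will occur.

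The conclusion does not rest on the incomplete sentence.

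**What to change.** 1. Reconcile exclusion 3 in 4.2, the opening of 5.6 and the two radiotherapy entries into one statement, and complete the sentence on local therapies if it is also incomplete in the source document. Which clinical permission to keep is for the sponsor; no view is given here.
2. Whichever permission is kept, state in 5.6 and 7.2 that a first complete or partial response cannot be established after a target lesion has been irradiated on study. A patient with no earlier response then counts as a non-responder.
3. Add a target/non-target field to the existing radiotherapy eCRF entry. The first radiotherapy entry in 5.6 does not ask which lesion was treated, so without this field affected patients may not be identifiable later.
4. For duration of response and PFS, keep patient-level RECIST 1.1 progression as the event. Add a sensitivity analysis for patients with an irradiated target lesion, for example radiotherapy as an event against censoring at the last prior scan. Censoring should not be the only analysis: palliative treatment is prompted by symptoms, so it is probably informative.

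This should be in force before stage 1 is read. The cost is protocol and SAP wording, one eCRF field and one sensitivity analysis. The downside is that an occasional genuine responder irradiated before the first scan counts as a non-responder, so the reported rate may be slightly lower.

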5.8.2 Storage and Handling

5.9.2.1 CDX-3379

CDX-3379 is shipped in insulated shippers and must be stored at 2 - 8°C (36 - 46°F) until use. Do not freeze CDX-3379 solutions. A temperature log must be kept to document the refrigerator temperature. If the temperature is not maintained, Celldex should be contacted.

CDX-3379 is not formulated with a preservative. Therefore, once the sterile vials are entered (i.e., needle puncture of the vial), the drug should be used as soon as possible (typically within 3 hours if kept at room temperature or within 6 hours if refrigerated; or in accordance with any applicable institutional guidance). Additional guidance regarding storage and handling of CDX-3379 will be provided on the pharmacy sheet provided by Celldex.

5.9.2.2 Trametinib

Store refrigerated at 2° to 8°C (36° to 46°F). Do not freeze. Dispense in original bottle. Do not remove desiccant. Protect from moisture and light. Do not place medication in pill boxes.

5.8.3 Dispensing of Study Drug

5.9.3.1 CDX-3379 Preparation

General notes regarding the preparation of CDX-3379:

- Only qualified personnel who are familiar with procedures that minimize undue exposure to them and to the environment should undertake the preparation, handling, and safe disposal of biotherapeutic agents.
- Aseptic technique should be employed in the preparation of all study drugs.
- CDX-3379 is expected to be free from, or essentially free from, visible particulates. Parenteral drug products should be inspected visually for particulate matter and discoloration prior to administration. If significant particulate matter is present or the solution is discolored, the vial should not be used.
- Refrigerated solutions should be equilibrated to room temperature prior to administration.
- Before use, the vial should be gently swirled to ensure uniform mixing of the contents. Solution should be gently withdrawn (avoiding foaming and excess shearing).

A designated member(s) of the investigational site's pharmacy staff with appropriate training and experience (i.e., the pharmacist) will prepare CDX-3379. The pharmacist(s) will be required to complete a Dosage Preparation Record to document the preparation process for each dose of CDX-3379. Additional guidance will be provided within a pharmacy sheet provided by Celldex.

Dose Calculation

Doses of CDX-3379 will be based on body weight in kilograms. Patients are to be weighed at the start of each cycle and the dose adjusted based on current body weight and rounded to the nearest mg of CDX-3379. Half milligrams (mgs) should be rounded up to the next mg of dose. If body weight is within $\pm 10\%$ of the baseline measurement, the baseline weight may be used for dose calculation and preparation.

Dose Preparation Steps

CDX-3379 is diluted with 0.9% (w/v) saline to a minimum final volume of 100 mL, in an appropriately sized polyolefin, IV infusion bag. The final CDX-3379 concentration in the admixture shall be maintained in the qualified range of 1.8 to 13.8 mg/mL. Diluted CDX-3379 is administered to the patient via IV infusion, through an IV administration set with a low protein binding, 0.2- μ m in-line filter.

CONFIDENTIAL

5.9.3.2 Trametinib

The investigator or responsible site personnel must instruct the subject or caregiver to take trametinib as per protocol. This study drug will be dispensed to the subject by authorized site personnel only. All dosages prescribed to the subject and all dose changes during the study must be recorded on the Dosage Administration Record eCRF. Trametinib with instructions for administration will be provided to subjects for self-administration at home, until their next scheduled study visit.

Study drugs must be received at the study site by a designated person, handled and stored safely and properly, and kept in a secure location. Upon receipt, the study drug should be stored according to the instructions specified on the drug labels. Storage conditions must be adequately monitored and appropriate temperature logs maintained as source data. Appropriate documentation of the subject specific dispensing process must be maintained. Bulk medication labels will be in the local language, will comply with the legal requirements of each country, and will include storage conditions for the drug but no information about the subject.

All drug supplies are to be used only for this protocol and not for any other purpose. Unless specifically instructed by Novartis, the Investigator must not destroy any drug labels, or any partly used or unused drug supply. Only after receiving a written authorization by Novartis, the Investigator/designee will send all the unused and partly used drug supplies as well as the empty containers to the address provided at the time of authorization for destruction.

Trametinib will be either sourced as local commercial supply or provided as global clinical open label supply. Global clinical open label supply will be provided in bottles. Study treatment labels will comply with the legal requirements of each country and will include storage conditions.

Novartis Drug Supply Management supplied treatments will also contain a unique medication number (corresponding to study treatment and strength).

Responsible site personnel will identify the study treatment package(s) to dispense by the medication number(s) assigned by IRT to the subject. If the label has 2 parts (base plus tear-off label), immediately before dispensing the package to the subject, site personnel will detach the tear-off part of the label from the package and affix it to the subject's source document.

